7.2.4. Shifts Relative to the Baseline Value

Shift tables will be presented by showing change in severity grade from baseline to the worst grade postbaseline for hematology and chemistry laboratory tests.

7.3. Body Weight and Vital Signs

Descriptive statistics will be provided by treatment group for body weight, BMI, and vital signs as follows:

- Baseline value
- Postbaseline maximum value
- Postbaseline minimum value
- Change and percentage change from baseline to postbaseline maximum value
- Change and percentage change from baseline to postbaseline minimum value.

A baseline value will be defined as the last available value collected on or prior to the date/time of first dose of any study drug. Change from baseline to a postbaseline visit will be defined as the postbaseline value minus the baseline value.

In the case of multiple values for the same visit, data will be selected for analysis as described in Section 3.8.3. No formal statistical testing is planned.

A by-subject listing of vital signs will be provided by subject ID number and time point in chronological order. Body weight, height, and BMI will be included in the vital signs listing, if space permits. If not, they will be provided separately.

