8.6.4. Other Safety Analyses

The number and incidence of participants developing ADAs at any time will be summarized. Vital signs and physical examination findings will be summarized at select time points. Details will be provided in the statistical analysis plan (SAP).

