7.2.1. Summaries of Numeric Laboratory Results

Descriptive statistics will be provided by treatment group for each laboratory test specified in the study protocol as follows:

- Baseline values
- Values at each postbaseline time point visit
- Postbaseline maximum value

- Postbaseline minimum value
- Change and percentage change from baseline at each postbaseline time point visit
- Change and percentage change from baseline to postbaseline maximum value
- Change and percentage change from baseline to postbaseline minimum value

A baseline laboratory value will be defined as the last measurement obtained on or prior to the date/time of first dose of any study drug. Change from baseline to a postbaseline visit will be defined as the postbaseline value minus the baseline value. The mean, median, Q1, Q3, minimum, and maximum values will be displayed to the reported number of digits; StD values will be displayed to the reported number of digits plus 1.

Median (Q1, Q3) of the observed values will be plotted using a line plot by treatment group and visit for the laboratory tests including but not limited to hemoglobin, platelet, and absolute neutrophil counts.

In the case of multiple values associated with a visit, data will be selected for analysis as described in Section 3.8.3.

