9. PHARMACODYNAMIC ANALYSES

Exploratory analyses may be performed to evaluate the association of each biomarker or combination of biomarkers with clinical outcomes. Additional details will be provided separately by the biomarker sciences group.

10. Changes From Protocol-Specified Analyses

There are no deviations from the protocol-specified analyses.

11. **REFERENCES**

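### SAP 7.3 summarizes vital signs by arm only as baseline and postbaseline extremes, not at the time points Protocol 8.6.4 commits to, and those extremes depend on time on treatment (minor)

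*SAP*

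**What the plan says.** Protocol 8.6.4 (Other Safety Analyses) states: "Vital signs and physical examination findings will be summarized at select time points". It leaves the details to the SAP.

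SAP 7.3 (Body Weight and Vital Signs) introduces its tables with "Descriptive statistics will be provided by treatment group for body weight, BMI, and vital signs as follows". The list has five rows: baseline, postbaseline maximum, postbaseline minimum, "Change and percentage change from baseline to postbaseline maximum value" and "Change and percentage change from baseline to postbaseline minimum value". Time points appear in one other place: "A by-subject listing of vital signs will be provided by subject ID number and time point in chronological order". The section defines change from baseline to a postbaseline visit and refers to the rule for several values at one visit, but no row uses either.

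For laboratory tests, SAP 7.2.1 lists "Values at each postbaseline time point visit" and by-visit changes as well as the extremes. SAP 7.2 also ends laboratory data at 30 days after the last dose, or the day before new anticancer therapy if that is earlier. SAP 7.3 states no cutoff, and SAP 3.8.2 gives analysis windows for laboratory and PRO data only.

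SAP Section 10 states: "There are no deviations from the protocol-specified analyses".

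**The concern.** There are two parts.

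First, the protocol's commitment is not carried out. An extreme over all of follow-up is not a time point, and a by-subject listing is not a summary by arm. In the SAP, physical examination appears only in the appended schedules of assessments.

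Second, the statistics that remain are awkward to read. Protocol 5.1.5 has vital signs recorded before each infusion or injection of each study treatment, and Protocol 4.1 lets treatment run until progression, loss of benefit or toxicity. The number of readings per participant therefore follows time on treatment. The largest of many readings is expected to exceed the largest of few, even when nothing has changed in the participant. If one arm were treated longer, its mean maximum would be higher and its mean minimum lower for that reason alone. A reader of the safety report would have no by-arm table at fixed times to set against this.

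**Working it through.** The plan states no figure on this point, so there is none to reproduce. The check has three steps.

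**1. Scheduled postbaseline vital-sign days.** Inputs: azacitidine on Days 1-7 of each 28-day cycle (Protocol Table 3); magrolimab/placebo on Days 1, 4, 8, 11, 15, 22, 29, 36, 43, 50 and 57, then every 14 days (Protocol Table 4). Day 1 is taken as baseline.

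- Cycles 1-3 contain 3 × 7 = 21 azacitidine days. The magrolimab/placebo days not already among them are Days 8, 11, 15, 22, 36, 43, 50 and 71, which is 8. Total 21 + 8 − 1 (Day 1) = 28.
- Each later cycle adds 7 azacitidine days and one separate magrolimab/placebo day (cycle Day 15), which is 8.
- After 6 cycles: 28 + 3 × 8 = 52. After 12 cycles: 28 + 9 × 8 = 100.

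**2. Expected maximum with no drug effect and no trend.** In units of the within-person SD, measured from the person's own mean, for n independent readings:

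E[max] = ∫ x · n · φ(x) · Φ(x)^(n−1) dx

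The baseline reading has expectation zero on this scale, so E[max] is also the expected change from baseline to the maximum. The minimum mirrors it. For correlated readings, an AR(1) series was simulated (20,000 replicates).

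| Through | n | Independent | Lag-1 correlation 0.5 | Lag-1 correlation 0.8 |
|---|---|---|---|---|
| 3 cycles (Day 84) | 28 | 2.01 | 1.89 | 1.59 |
| 4 cycles (Day 112) | 36 | 2.12 | 2.02 | 1.73 |
| 6 cycles (Day 168) | 52 | 2.26 | 2.18 | 1.93 |
| 9 cycles (Day 252) | 76 | 2.41 | 2.34 | 2.12 |
| 12 cycles (Day 336) | 100 | 2.51 | 2.45 | 2.25 |

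At a fixed time point the corresponding expectation is 0, whatever the time on treatment.

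**3. Difference between arms if exposure differs.** The documents give no exposure by arm, so these contrasts are assumptions.

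- Everyone in one arm treated to Day 168 and everyone in the other to Day 336: 2.51 − 2.26 = 0.25 SD with independent readings, and 2.25 − 1.93 = 0.32 SD at correlation 0.8.
- Exponential treatment durations with medians of 4 and 8 cycles: about 0.23 SD with independent readings, and about 0.26 to 0.29 SD at correlations 0.5 and 0.8.

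Correlation lowers the level of the expected maximum, but in these scenarios it does not shrink the difference between arms.

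Cutting the extremes off at Day 168 in the second scenario leaves about 0.12 to 0.13 SD with independent readings, roughly half. Participants who stop early still have fewer readings.

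**The case against.** The case for leaving SAP 7.3 alone has real content.

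- **The protocol defers to the SAP, and Protocol 8.6 allows safety data in general to be graphed, summarized or listed.** This lets the SAP choose which time points. It does not turn the specific commitment in 8.6.4 into none, and 8.6.4 speaks of summaries.
- **The listing shows readings by time point.** It does, so the individual data are reported. It does not compare the arms.
- **Extremes are a standard safety display, and the laboratory section uses them too.** True. They are acceptable beside by-visit tables, which is how SAP 7.2.1 presents them.
- **The output is descriptive.** SAP 7.3 plans no formal testing. No endpoint, alpha allocation or stopping boundary is touched. This stands and limits the weight of the point.

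A reader might also infer more than the documents support:

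- **That noise produces a large spurious treatment effect.** At an assumed systolic SD of 8 to 15 mmHg, the change to the maximum after 6 cycles is about 2.27 × 8 = 18 to 2.27 × 15 = 34 mmHg. That shift is expected in both arms and largely cancels between them.
- **That one arm will in fact look worse.** This needs unequal time on treatment, and nothing in the documents shows it.
- **That weight and BMI are affected to the same degree.** Weight is taken on Day 1 of each cycle or every 4 weeks, so the counts above do not apply. The missing time points do.
- **That early reactions to infusion go unseen.** Scheduled vital signs are predose, so by-visit tables would not show acute infusion effects. SAP 7.1.7.1 already tabulates infusion-related reactions, anaemia and thromboembolic events by time of first onset, including the first 2 weeks.

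**Conclusion.** The point holds as a minor one. The mismatch between Protocol 8.6.4 and SAP 7.3, the missing physical examination summary, and the Section 10 statement that nothing departs from the protocol can all be read directly from the text and rest on no assumption.

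The dependence of the vital-sign extremes on the number of readings is also certain in direction. Its effect on the comparison of arms is conditional: about 0.23 to 0.29 within-person SD, upward for the maximum and downward for the minimum, if median treatment were 4 versus 8 cycles. That range assumes exponential durations, dosing on schedule, no drug effect or trend, and readings either independent or serially correlated up to 0.8. With equal exposure the difference between arms vanishes, although the mean change to each extreme is still not zero.

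**What to change.** In SAP 7.3:

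- Add observed value and change from baseline, with n, by treatment group at named scheduled visits for vital signs and weight.
- Add vital-sign visit windows to SAP 3.8.2 that keep the early scheduled days apart. The laboratory windows in Table 3-1 should not be reused: their Week 1 window runs from the first dose to Day 11, and SAP 3.8.3 keeps the record nearest Day 8 when one value is needed, so the Day 4 and Day 11 readings would drop out.
- State an on-treatment data cutoff, as SAP 7.2 does.
- Keep the maximum and minimum rows as supplementary and label them exposure-dependent. A 24-week cap is not a substitute, since about half of the assumed difference would remain.
- Note under the tables that by-visit means describe participants still under observation at that visit.

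Add a physical examination summary, or record its removal in SAP Section 10.

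The cost is SAP wording and a few extra descriptive tables from data already scheduled for collection.

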7.4. Prior and Concomitant Medications

Medications collected at screening and during the study will be coded using the current version of the World Health Organization (WHO) Drug dictionary.

7.4.1. **Prior Medications**

Prior medications are defined as any medications taken before a subject takes the first study drug.

Prior medications will be summarized by Anatomical Therapeutic Chemical (ATC) drug class Level 2 preferred name using the number and percentage of patients for each treatment group and overall. A subject reporting the same medication more than once will be counted only once when calculating the number and percentage of patients who received that medication. The summary will be ordered alphabetically by ATC medical class and then by preferred term in order of descending overall frequency within each ATC medical class. For drugs with the same frequency, sorting will be done alphabetically.

For the purposes of analysis, any medication with a start date prior to the first dosing date of study drug will be included in the prior medication summary regardless of when the stop date is. If a partial start date is entered the medication will be considered prior unless the month and year (if day is missing) or year (if day and month are missing) of the start date are after the first dosing date. Medications with a completely missing start date will be included in the prior medication summary, unless otherwise specified.

Summaries will be based on the Safety Analysis Set. No formal statistical testing is planned.

7.4.2. Concomitant Medications

Concomitant medications are defined as medications taken while a subject took study drug. Use of concomitant medications will be summarized by ATC drug class Level 2 preferred name using the number and percentage of patients for each treatment group. A subject reporting the same medication more than once will be counted only once when calculating the number and percentage of patients who received that medication. The summary will be ordered alphabetically by ATC medical class and then by preferred term in descending overall frequency within each ATC medical class. For drugs with the same frequency, sorting will be done alphabetically.

For the purposes of analysis, any medications with a start date prior to or on the first dosing date of study drug and continued to be taken after the first dosing date, or started after the first dosing date but prior to or on 70 days after last dosing date of study drug will be considered concomitant medications. Medications started and stopped on the same day as the first dosing date or 70 days after the last dosing date of study drug or a start date after the last dosing date of study drug will also be considered concomitant. Medications with a stop date prior to the date of first dosing date of study drug or a start date after the last dosing date of study drug plus 70 days will be excluded from the concomitant medication summary. If a partial stop date is entered, any medication with the month and year (if day is missing) or year (if day and month are missing) prior to the date of first study drug administration will be excluded from the concomitant medication with the month and year (if day is missing) or year (if day and month are missing) after the study drug stop date plus 70 days will be excluded from the concomitant medication summary. Medications with completely missing start and stop dates will be included in the concomitant medication summary. Medications with completely missing start and stop dates will be based on the Safety Analysis Set. No formal statistical testing is planned.

All prior and concomitant medications (other than per-protocol study drugs) will be provided in a by-subject listing sorted by subject ID number and administration date in chronological order.

7.5. Premedication

Premedication is required prior to the administration of the first 4 doses of magrolimab/placebo and in case of repriming. Premedication during subsequent infusions may be continued based on the treating physician's clinical judgment and the presence/severity of prior infusion-related reactions. In the case of a Grade 3 infusion-related reaction, a premedication regimen for subsequent infusions is required.

Premedications will be summarized by Anatomical Therapeutic Chemical (ATC) drug class Level 2 preferred name using the number and percentage of patients for each treatment group and overall. A subject reporting the same medication more than once will be counted only once when calculating the number and percentage of patients who received that medication. The summary will be ordered alphabetically by ATC medical class and then by preferred term in order of descending overall frequency within each ATC medical class. For drugs with the same frequency, sorting will be done alphabetically.

7.6. Electrocardiogram Results

A by-subject listing of ECG results will be provided by subject ID number in ascending order.

7.7. Other Safety Measures

A by-subject listing of ECOG performance status will be provided by subject ID number in ascending order.

8. PHARMACOKINETIC (PK) AND IMMUNOGENECITY ANALYSES

8.1. PK Sample Collection

Blood samples for evaluating magrolimab serum concentrations will be collected at pre-dose at Day 1, Day 8, Day 29, Day 57, Day 113, Day 169, Day 253, Day 337, and EOT.

8.2. PK Analyses

Magrolimab concentration will be summarized for the PK Analysis Set. The individual subject's concentration data for magrolimab will be listed based on the sampling time point. Magrolimab PK data will be summarized per nominal time point using descriptive statistics. Summary statistics (n, mean, SD, coefficient of variation [%CV], median, min, max, Q1, Q3, and geometric mean) will be presented for magrolimab serum concentration data at each time point.

The sample size (number of patients) at each time point will be based on the number of patients with nonmissing concentration data at that time point. Missing concentration values will be reported as is in data listings. Values that are BLQ will be treated as 0 at predose and postdose time points for summary purposes, and reported as-is in data listings.

Descriptive graphical plots of individual serum concentration versus time profiles and mean (StD) concentration versus nominal time profiles will be generated.

Due to the sparse nature of PK collection, PK parameters will not be calculated.

Data from this study may be combined with PK data from other magrolimab clinical studies and analyzed using a population PK model. Such an analysis will be reported separately.

8.3. Immunogenicity Analysis

The rate and magnitude of antimagrolimab antibody prevalence, incidence, persistence, and transience will be summarized for the Immunogenicity Analysis Set. Neutralizing antibody incidence will also be summarized.

ADA Prevalence: the proportion of subjects who had at least one positive ADA sample (baseline or post-baseline) based on the Immunogenicity Analysis Set.

Treatment-Induced ADA Rate: the proportion of subjects who had negative baseline ADA sample and at least one positive post-treatment ADA sample based on subjects who had both non-missing baseline and at least one post-treatment ADA result reported (i.e. ADA Incidence Analysis Set).

Treatment-Boosted ADA Rate: the proportion of subjects who had positive baseline ADA sample and at least one positive post-treatment ADA sample and the (max titer of the post-treatment ADA) / (titer of baseline ADA) \geq 4 based on the ADA Incidence Analysis Set

ADA Incidence (treatment-emergent ADA): the proportion of subjects who had treatmentinduced or treatment-boosted ADA based on subjects who had non-missing baseline ADA sample and at least one post-treatment ADA result reported in Immunogenicity Analysis Set.

Persistent ADA is defined as:

a) Treatment-Induced ADA detected at two or more sampling time points during the treatment (including follow-up period if any), where the first and last ADA-positive sample (irrespective of any negative samples in between) are separated by a period of 16 weeks or longer.

or

b) Treatment-Induced ADA detected in the last sampling time point of the treatment study period.

ADA Persistence Rate: the proportion of subjects who had persistent ADA based on the ADA Incidence Analysis Set.

Transient ADA is defined as:

Treatment-Induced ADA that does not meet the definition of persistent ADA. The proportion of subjects who had transient ADA is based on the subjects evaluable for ADA incidence.

Neutralizing antibody (NAb) Incidence: the proportion of subjects who had at least one positive neutralizing antibody result reported based on the treatment-emergent ADA (treatment-induced or treatment-boosted ADA) among the subjects evaluable for ADA incidence.

Titer summaries may also be generated, if relevant. Exploratory evaluations may be conducted to determine the relationship between anti-magrolimab antibody positivity and safety, PK, or efficacy parameters (eg, drug concentrations, AEs, or disease response) using graphical, and/or tabular approaches.

9. PHARMACODYNAMIC ANALYSES

Exploratory analyses may be performed to evaluate the association of each biomarker or combination of biomarkers with clinical outcomes. Additional details will be provided separately by the biomarker sciences group.

10. Changes From Protocol-Specified Analyses

There are no deviations from the protocol-specified analyses.

11. **REFERENCES**

12. SOFTWARE

SAS® Software Version 9.4. SAS Institute Inc., Cary, NC, USA.

13. SAP REVISION

Revision Date (DD MMM YYYY)	Section	Summary of Revision	Reason for Revision

14. **APPENDICES**

Appendix 1.Schedule of AssessmentsAppendix 2.Disease Response Assessm

ppendix 2. Disease Response Assessment Based on International Working Group Criteria

Appendix 1. Schedule of Assessments

Appendix Table 1. Schedule of Assessments – Screening

	Study 5F9009
Assessment	Day -30 to1
Informed consent	Xª
Demographics	Х
Medical and cancer history	Х
Pregnancy test	X ^b
Serum or plasma chemistry	Х
Serum uric acid, phosphorus	Х
Hematology ^d	Х
Blood phenotyping or genotyping, type, and screen (ABO/Rh), DAT ^e	Х
Urinalysis	Х
Bone marrow biopsy and aspirate for blast evaluation, biomarker studies, cytogenetics, and MRD assessment ^c	Х
ECOG	Х
Vital signs, height, and weight	Х
Complete physical examination	Х
ECG (single)	Х
Hepatitis B, hepatitis C, and HIV ^f	Х
Adverse events related to protocol-mandated procedures	Х
Concomitant medications	Х
Entry criteria	Х
Randomization	Xa

Abbreviations: ABO = any of the 4 blood groups A, B, AB, and O comprising the ABO system; DAT = direct antiglobulin test; ECG = electrocardiogram; ECOG = Eastern Cooperative Oncology Group; FSH = follicle-stimulating hormone; MRD = minimal residual disease; Rh = Rhesus factor; SOC = standard of care.

- a Screening must be completed before randomization. Randomization must occur within 30 days of signing informed consent. The first dose of study treatment (Protocol Table 3 and Protocol Table 4) must be given within 72 hours after randomization.
- b Screening pregnancy test may be used as the Day 1 test if performed within 72 hours of first dose; additional guidance is provided in Protocol Section 5.1.1. FSH test is required for female patients who are < 54 years old who are not on hormonal contraception and who have stopped menstruating for \geq 12 months but do not have documentation of ovarian hormonal failure.
- c A trephine (biopsy) is to be collected for baseline. A bone marrow biopsy collected per SOC within 30 days of randomization can be considered the screening sample, and shipped to central laboratory. This procedure must be performed prior to the first dose of study treatment at the latest. An aspirate sample must be collected at the screening visit for blast evaluation, MRD assessment, biomarker studies, baseline for response assessment and biobanking. It is preferred that bone marrow aspirate samples are obtained at the time of bone marrow (trephine) biopsy. Conventional cytogenetics to be tested per institutional standards.
- d Hematology analytes to be assessed at screening are provided in Protocol Table 7
- e RBC genotyping (instead of an extended RBC phenotyping) must be performed if a patient received any RBC or whole blood transfusion within the previous 3 months (unless laboratory has availability for special techniques for performing phenotyping for patients with recent transfusion). Results must be available before the first dose of magrolimab.
- f Refer to Exclusion Criteria 13 and Other Laboratory Measurements in Protocol Table 7

		Cycle (28-day Cycles)																			
				1							2				3+						
Visit Window (Days)	No	ne			± 3						±3						± 3				
Cycle Day	1	2	3	4	5	6	7	1	2	3	4	5	6	7	1	2	3	4	5	6	7
PRO assessment ^a	X							Х							Х						
CBC with differential, platelets, reticulocytes ^b	X							Х							Х						
Serum or plasma chemistry ^b	X							Х							Х						
Bone marrow biopsy and aspirate for biomarker studies ^c															X ^{d,e}						
Bone marrow aspirate biopsy for MRD monitoring, cytogenetics, and response assessment ^{d,f}															X Q2C, Q3C ^e						
Vital signs ^g	X	X	X	X	X	X	X	Х	X	X	X	X	X	X	Х	X	X	X	X	X	X
Symptom-directed physical examination ^b	X							Х							Х						
Adverse events	X	X	X	X	X	Χ	X	Х	X	X	X	Х	X	X	Х	X	X	X	X	X	X
Blood transfusion	X	X	X	X	X	X	X	Х	X	X	X	Χ	X	X	Х	X	X	X	X	X	X
Concomitant medications	X	X	X	X	X	X	X	Х	X	X	X	Χ	X	X	Х	X	X	X	X	X	X
Azacitidine ^h	X	X	X	X	Χ	Χ	X	Х	X	X	X	Х	Χ	X	Х	X	X	X	X	X	X

Appendix Table 2. Schedule of Assessments - Treatment Period-Azacitidine Dosing and Study Assessments

Abbreviations: CBC = complete blood count; EQ-5D-5L = 5-level EuroQol 5 dimensions; FACT-Anemia = Functional Assessment of Cancer Therapy-Anemia; MRD = minimal residual disease; PGIC = Patient Global Impression of Change; PGIS = Patient Global Impression of Severity; PRO = patient-reported outcome; Q2C = every 2 cycles; Q3C = every 3 cycles.

- a Four PRO questionnaires will be administered in this study: the FACT-Anemia questionnaire, the EQ-5D-5L, the PGIS, and the PGIC. The patient should complete these questionnaires before other study procedures at required visits. No PGIC assessment at Cycle 1 Day 1. FACT-Anemia and EQ-5D-5L should be implemented prior to PGIS/PGIC.
- b If magrolimab and azacitidine are administered on the same day, only one such study assessment is needed. Assessments should be performed prior to study treatment administration. Pretreatment assessments for the initial dose (Cycle 1 Day 1) may be collected up to 72 hours before administration of study treatment; thereafter, pretreatment assessments are to be collected within 24 hours prior to study treatment administration.
- c Bone marrow biopsy samples will be collected at Day 1 of Cycles 3 and 10.
- d An aspirate sample will be collected for response assessment, biomarker studies, and MRD assessment. Conventional cytogenetics to be tested per institutional standards. Response assessments may be adjusted by ± 1 week for Cycle 3 Day 1. After Cycle 3 Day 1, the window is ± 14 days.
- e An aspirate sample will be collected for biomarker studies at Day 1 of Cycles 3, 5, 7, 10, and 13.
- f Samples will be collected at Day 1 of Cycles 3, 5, and 7 and then every 3 cycles thereafter during study treatment. Bone marrow aspirate biopsies for response assessments may be adjusted by \pm 1 week for Cycle 3 Day 1. After Cycle 3 Day 1, the window is \pm 14 days.
- g Vital signs will be assessed prior to infusion/injection of each study treatment. Weight will be assessed on Day 1 of each cycle. Details are provided in Protocol Section 5.1.5.
- h If Azacitidine and magrolimab/placebo are administered on the same day, azacitidine administration should be completed at least 1 hour before magrolimab/placebo administration. Azacitidine may be administered on an alternative schedule of Days 1 to 5, Day 8, and Day 9 of a 28-day cycle for flexibility and convenience.

Dose Schedule		Priming Dosing				Μ	aintenance Dosing										
Visit Window (Days)	No	ne					±	3					±3				
Day	1	2	4	8	11	15	22	29	36	43	50	57	every 2 Weeks thereafter				
Pregnancy test ^a	X							X				X Q4W					
CBC with differential, platelets, reticulocytes ^{b,c,d}	Xe	X	Xe	X	X	X	X	X	X	X	X	Х	Х				
Haptoglobin and LDH ^c	X			X				X									
Serum or plasma chemistry ^{b,c}	X			X		X	X	X		X		Х	X				
Peripheral smear ^{c,f}	X	X			X												
Peripheral blood sample for biomarker studies ^g	X			X				X				X ^h					
PK ^g	X			X				X				Xi					
Antidrug antibodies ^{c,j}	X							X				\mathbf{X}^{i}					
Vital signs ^k	X		X	X	X	X	X	X	X	X	X	Х	X				
Symptom-directed physical examination ^{b,c}	X			X		X		X				Х	X				
Adverse events	X	X	X	X	X	X	X	X	X	X	X	Х	X				
Blood transfusion	X	X	X	X	X	X	X	X	X	X	X	Х	X				
Concomitant medications	X	X	X	X	X	X	X	X	X	X	X	Х	X				
Premedication ¹	X		X	X	X												
Magrolimab or placebo ^m	Xn		Xn	X	X	X	X	X	X	X	X	Х	X				

Appendix Table 3. Schedule of Assessments - Treatment Period-Magrolimab or Placebo Dosing and Study Assessments

Abbreviations: CBC = complete blood count; D = day; EOT = end of treatment; LDH = lactate dehydrogenase; MRD = minimal residual disease; PK = pharmacokinetic(s); PRO = patient-reported outcome; Q4W = every 4 weeks; WBC = white blood cell.

a Screening pregnancy test may be used if performed within 72 hours of first dose; pregnancy tests will be conducted once every month; additional guidance is provided in Protocol Section 5.1.1.

b If magrolimab and azacitidine are administered on the same day, only one such study assessment is needed Assessments should be performed prior to study treatment administration. For monitoring of infusion-related reactions, please refer to Protocol Section 6.5

- c Pretreatment assessments for the initial dose may be collected up to 72 hours before administration of study treatment; thereafter, pretreatment assessments are to be collected within 24 hours prior to study treatment administration.
- d Additional samples for CBC may be collected outside of the protocol-specified time points to ensure a WBC level $\leq 20 \times 103/\mu$ L prior to each magrolimab/placebo dose during the first 28 days of magrolimab priming dose. Peripheral blasts should be included in the CBC assessments.
- e An additional hemoglobin check must be performed 3 to 6 hours after the initiation of the first and second doses of magrolimab/placebo during initial treatment. The patient should be transfused as clinically appropriate. Investigators should consider additional hemoglobin monitoring during the first week of treatment in patients with symptoms of anemia or increased risk for complications of anemia.
- f Peripheral smears will be collected predose and assessed locally.
- g Samples for PK and biomarker studies will be collected predose within 12 hours prior to study treatment administration.
- h Samples will be collected prior to first maintenance dose (Day 57), ninth (Day 169) maintenance dose, and EOT.
- i Samples will be collected predose on Day 57, Day 113, Day 169, Day 253, Day 337, and EOT.
- j When collected on the day of study treatment dosing, the blood sample for antidrug antibodies must be collected at the same time as the predose PK sample.
- k Vital signs will be assessed prior to infusion/injection of each study treatment. Weight will be assessed every 4 weeks. Details are provided in Protocol Section 5.1.5.
- Premedication is required prior to the administration of the first 4 doses of study treatment and in case of reintroduction with reprining. Premedication for subsequent treatment periods may be continued based on the treating physician's clinical judgment and the presence/severity of prior infusion-related reactions. In the case of a Grade 3 infusion-related reaction, a premedication regimen for subsequent treatment periods is required (Protocol Section 6.5).
- m Magrolimab or saline placebo should not be given on consecutive days. The duration of each magrolimab/placebo infusion including flush will be 3 hours (± 30 minutes) for the first dose of treatment. After the first dose of treatment, the magrolimab/placebo infusion including flush will be 2 hours (± 30 minutes). All patients should be monitored for 1 hour after infusion for doses during the first 28 days and the repriming doses.
- n Within 24 hours prior to each of the first 2 doses of magrolimab/placebo infusion during initial treatment, all subjects must have a documented hemoglobin ≥ 9.0 g/dL. Patients who do not meet these criteria must be transfused and have their hemoglobin rechecked to meet 9.0 g/dL prior to each of the first 2 doses of magrolimab.

Appendix Table 4.	Schedule of Assessments – Post Treatment
-------------------	--

	End-of- treatment Visit	Safety Follow (Telep	-up Visit/Call hone)ª	Long-term Follow-up	Survival Follow-up
	Within 7 Days after Last Dose or EOT Decision	30 Days after Last Dose	70 Days after Last Dose ^k	Until Start of New Anticancer Therapy or Transformation to AML ^b	Every 2 Months Until Death or End of Study
Visit Window	±7 Days	±7 Days	±7 Days	+4 Weeks	
Serum or urine pregnancy test	Х			Q4W ^c	Q4W ^c
CBC with differential, platelet count, reticulocytes	X			Q8W ^d	
Serum or plasma chemistry	X				
Peripheral blood for biomarker studies	Х				
Pharmacokinetics	Х				
Antidrug antibodies	Х				
Bone marrow biopsy and aspirate for MRD monitoring and cytogenetics ^{d,e}	Х			Q8W ^d	
Response assessment ^{e,f}	Х			Q8W ^d	
ECOG	Х				
Vital signs	Х				
Symptom-directed physical examination	Х				
PRO assessment ^g	Х			Х	
Adverse events ^h	Х	Х	Х		
Concomitant medications	Х	Х	Х		
Blood transfusion ⁱ				Х	Х
New anticancer therapy ^j				Х	Х
Survival follow-up					Q2M

Abbreviations: AE = adverse event; AML = acute myeloid leukemia; CBC = complete blood count; CR = complete remission; eCRF = electronic case report form; EOT = end of treatment; EQ-5D-5L = 5-level EuroQol 5 dimensions; FACT-Anemia = Functional Assessment of Cancer Therapy-Anemia; IWG = International Working Group; MDS = myelodysplastic syndrome; MRD = minimal residual disease; PGIC = Patient Global Impression of Change; PGIS = Patient Global Impression of Severity; PR = partial remission; PRO = patient-reported outcome; QxM = every x months; QxW = every x weeks; SAE = serious adverse event.

- a If the patient experiences a treatment-related AE or an SAE (regardless of attribution), the patient must be asked to come to the site.
- b Until start of new anticancer therapy or transformation to AML, whichever comes first.
- c Collect until the end of the contraception requirement.
- d Bone marrow assessment, MRD, CBC, and response assessment should be performed until start of new anticancer therapy or transformation to AML, whichever comes first. Conventional cytogenetic testing (per institutional standards) is required for all patients.
- e For patients who come off the study treatment to undergo a stem cell transplant, response assessments for relapse/remission status and bone marrow aspirate results are required to be obtained locally and entered into the eCRF.
- f Response assessment at EOT visit not required if performed within the last 30 days or progressive disease has been documented. After disease progression (including treatment failure by IWG criteria and relapse after CR or PR), response assessment will focus on evaluation of transformation to AML.
- g Paper PROs will be administered in this study: The FACT-Anemia questionnaire, the EQ-5D-5L, the PGIS, and the PGIC will be administered. The patient should complete these questionnaires before other study procedures at required visits. FACT-Anemia and EQ-5D-5L should be implemented prior to PGIS/PGIC-FACT-Anemia, EQ-5D-5L the PGIS, and the PGIC should also be collected during long-term follow-up prior to initiation disease progression or initiation of a new anticancer therapy.
- h Report all AEs through the Safety Follow-up Visit/Call and any treatment-related SAEs thereafter.
- i Collect blood transfusions until start of new anticancer therapy.
- j Collect new anticancer therapy data following the last dose of study treatment.
- k For patients who do not initiate new anticancer therapy after the last dose. See Protocol Sections 5.1.10 for adverse event reporting details.

Appendix Table 5. Schedule of Assessments – Repriming (Required After > 4 Weeks Have Lapsed Since the Last Dose of Magrolimab/Placebo Delays)

						Day					
	1	2	3	4	5	6	7	8	11	15	22
Visit Window (Days)	-	-	± 3	± 3	± 3	± 3	± 3	± 3	± 3	± 3	± 3
Pregnancy test	X										
CBC with differential, platelets, and reticulocytes ^{a,b}	X	X		X				Х	X	X	X
Haptoglobin and LDH	X							X			
Serum or plasma chemistry ^a	X							Х		X	Х
Peripheral smear ^{a,c}	X	X							X		
Peripheral blood for biomarker studies ^d	X							X			
PK ^d	X							Х			
Antidrug antibodies ^a	X										
Vital signs ^e	X	X						X		X	X
Symptom-directed physical examination ^a	X							Х		X	
Adverse events	X	X	X	X	X	X	X	Х	X	X	Х
Concomitant medications	X	X	X	X	X	X	X	Х	X	X	Х
Blood transfusions	X	X	X	X	X	X	X	Х	X	X	Х
Premedication ^f	X			X				Х	X		
Magrolimab/placebo: repriming ^g	X			X				Х	X	X	Х

Abbreviations: CBC = complete blood count; ECOG = Eastern Cooperative Oncology Group; LDH = lactate dehydrogenase; PK = pharmacokinetic(s); PRO = patient-reported outcome; WBC = white blood cell.

a Pretreatment assessments are to be collected within 24 hours prior to study treatment administration.

b Additional samples for CBC may be collected outside of the protocol-specified time points to ensure a WBC level $\leq 20 \times 10^3/\mu$ L for the repriming cycle.

c Peripheral smears will be collected and assessed locally.

d Samples for PK and biomarker studies will be collected predose within 12 hours prior to study treatment administration.

- e Vital signs prior to infusion/injection of study treatment. Weight at Day 1. Details are provided in Protocol Section 5.1.5.
- f Premedication is required prior to the administration of the first 4 doses of study treatment and in case of reintroduction with repriming. Premedication for subsequent cycles may be continued based on the treating physician's clinical judgment and the presence/severity of prior infusion-related reactions. In the case of a Grade 3 infusion-related reaction, a premedication regimen for subsequent cycles is required (Protocol Section 6.5).
- g Magrolimab or saline placebo should not be given on consecutive days. During repriming, the duration of each magrolimab/placebo infusion including flush will be 3 hours (± 30 minutes) for the first 3 doses of treatment and 2 hours (± 30 minutes) for infusions beyond the first 3 doses. All participants should be monitored for 1 hour after infusion for doses during the first 28 days and the repriming doses. After Day 22, participants should return to their original dose schedule.

